#### **Medical Conditions:**

1. Evidence or history of clinically significant hematological, renal, endocrine, pulmonary, gastrointestinal, cardiovascular, hepatic, psychiatric, neurological, or allergic disease (including drug allergies, but excluding untreated, asymptomatic, seasonal allergies at the time of dosing).

2. Any condition possibly affecting drug absorption (eg, gastrectomy, cholecystectomy).
3. Known immunodeficiency disorder, including positive serology for HIV, or a first degree relative with a hereditary immunodeficiency.
4. Infection with hepatitis B or hepatitis C viruses according to protocol specific testing algorithm.
5. a. For hepatitis B, all participants will undergo testing for HBsAg and HBcAb.
  - If HBsAg is positive, the participant must be excluded from participation in the study.
  - If HBsAg and HBcAb are both negative, the participant is eligible for study inclusion.
  - If HBsAg is negative and HBcAb is positive, HBsAb should be evaluated:
    6. i. If HBsAb is negative, the participant must be excluded from participation in the study;
    7. ii. If HBsAb is positive, the participant is eligible for study inclusion.
8. b. For hepatitis C, all participants will undergo testing for HCVAb. Only participants who are HCVAb negative are eligible.
9. Participants with any of the following acute or chronic infections or infection history:
  - Any infection requiring treatment within 2 weeks prior to dosing.
  - Any infection requiring hospitalization or parenteral antimicrobial therapy within 60 days of the first dose of study intervention.
  - Any infection judged to be an opportunistic infection or clinically significant by the investigator, within the past 6 months of the first dose of study intervention.
  - Known active or history of recurrent bacterial, viral, fungal, mycobacterial or other infections.
  - History of recurrent (more than one episode of) localized dermatomal herpes zoster, or history of disseminated (single episode) herpes simplex or disseminated herpes zoster.
10. History of febrile illness within 5 days prior to the first dose of study intervention.

11. History of any lymphoproliferative disorder such as EBV related lymphoproliferative disorder, history of lymphoma, history of leukemia, or signs or symptoms suggestive of current lymphatic or lymphoid disease.
12. Known present or a history of malignancy other than a successfully treated or excised nonmetastatic basal cell or squamous cell cancer of the skin or cervical carcinoma in situ.
13. Evidence of untreated or inadequately treated active or latent *Mycobacterium TB* infection as evidenced by the following:
  - A positive QFT-G test performed within the 12 weeks prior to screening. If the laboratory reports the test as indeterminate, the test should be repeated. If the result of the repeat test is indeterminate, a PPD test may be substituted for the QFT-G test only with approval from the Pfizer Medical Monitor on a case-by-case basis.
  - History of either untreated or inadequately treated latent or active TB infection.
    - If a participant has previously received an adequate course of therapy for either latent (9 months of isoniazid in a locale where rates of primary multi-drug resistant TB infection are <5% or an acceptable alternative regimen) or active (acceptable multi-drug regimen) TB infection, neither a QFT-G test nor a PPD test need be obtained. Details of the previous course of therapy (eg, medication(s) used, dose, duration of therapy) should be documented in the source documentation.
    - A participant who is currently being treated for active or latent TB infection must be excluded from the study.
14. Other medical or psychiatric condition including recent (within the past year) or active suicidal ideation/behavior, laboratory abnormality or other conditions that may increase the risk of study participation or, in the investigator's judgment, make the participant inappropriate for the study.

#### **Prior/Concomitant Therapy:**

15. Use of prescription or nonprescription drugs and dietary and herbal supplements within 7 days or 5 half-lives (whichever is longer) prior to the first dose of study intervention. (Refer to [Section 6.9](#) Prior and Concomitant Therapy for additional details).
16. Use of injectable hormone therapy (eg, DepoProvera®) within 6 months prior to the first dose of study intervention.

17. Vaccination with live attenuated replication-competent vaccine within the 6 weeks prior to the first dose of study intervention. (Refer to [Section 5.3.5](#) for additional details).

#### **Prior/Concurrent Clinical Study Experience:**

18. Previous administration of an investigational product (drug or vaccine) within 30 days (or as determined by the local requirement) or 5 half-lives preceding the first dose of study intervention used in this study (whichever is longer).

#### **Diagnostic Assessments:**

19. A positive urine drug test.
20. A positive serum pregnancy test.
21. Screening supine BP  $\geq$ 140 mm Hg (systolic) or  $\geq$ 90 mm Hg (diastolic), following at least 5 minutes of supine rest. If BP is  $\geq$ 140 mm Hg (systolic) or  $\geq$ 90 mm Hg (diastolic), the BP should be repeated 2 more times and the average of the 3 BP values should be used to determine the participant's eligibility.
22. Participants with ANY of the following abnormalities in clinical laboratory tests at screening or Day -1, as assessed by the study-specific laboratory and confirmed by a single repeat test, if deemed necessary:
  - AST or ALT level  $> 1.5 \times$  ULN;
  - Total bilirubin level  $> 1.5 \times$  ULN; participants with a history of Gilbert's syndrome may have direct bilirubin measured and would be eligible for this study provided the direct bilirubin level is  $\leq$  ULN;
  - Hemoglobin level  $< 120 \text{ g/L (12.0 g/dL)}$ ;
  - Platelet count  $< 150 \times 10^9/\text{L (150,000 cells/mm}^3)$ ;
  - ANC  $< 1.2 \times 10^9/\text{L (1200 cells/mm}^3)$ ;
  - ALC  $< 0.8 \times 10^9/\text{L (800 cells/mm}^3)$ ;
  - eGFR  $< 75 \text{ mL/minute/1.73 m}^2$  based on the CKD-EPI equation;
  - In the opinion of the investigator or Pfizer (or designee), have any clinically significant laboratory abnormality that could affect interpretation of study data or the participant's participation in the study.

### **Other Exclusion Criteria:**

23. History of alcohol abuse or binge drinking and/or any other illicit drug use or dependence within 6 months of Screening. Binge drinking is defined as a pattern of 5 (male) and 4 (female) or more alcoholic drinks in about 2 hours. As a general rule, alcohol intake should not exceed 14 units per week (1 unit = 8 ounces (240 mL) beer, 1 ounce (30 mL) of 40% spirit, or 3 ounces (90 mL) of wine).
24. Blood donation (excluding plasma donations) of approximately 1 pint (500 mL) or more within 60 days prior to dosing.
25. Use of tobacco/nicotine containing products in excess of 5 cigarettes/day.
26. History of severe allergic or anaphylactic reactions.
27. WOCBP who are unwilling or unable to use an acceptable method of contraception as outlined in [Section 10.4](#) during the intervention period and for at least 28 days after the last dose of study intervention.
28. Females on HRT and whose menopausal status is in doubt.
29. Unwilling or unable to comply with the criteria in the Lifestyle Considerations section of this protocol.
30. Investigator site staff directly involved in the conduct of the study and their family members, site staff otherwise supervised by the investigator, and sponsor and sponsor delegate employees directly involved in the conduct of the study and their family members.

### **5.3. Lifestyle Considerations**

The following guidelines are provided:

#### **5.3.1. Contraception**

The investigator or their designee, in consultation with the participant, will confirm that the participant is utilizing an appropriate method of contraception for the individual participant and their partner(s) from the permitted list of contraception methods (see [Appendix 4](#), [Section 10.4.4](#)) and will confirm that the participant has been instructed in its consistent and correct use. At time points indicated in [SoA](#), the investigator or designee will inform the participant of the need to use acceptable effective contraception consistently and correctly and document the conversation and the participant's affirmation in the participant's chart. Participants need to affirm their consistent and correct use of at least 1 of the selected methods of contraception, considering that their risk for pregnancy may have changed since the last visit.

In addition, the investigator or designee will instruct the participant to call immediately if the selected contraception method is discontinued and document the requirement to use an

alternate protocol-specified method, including if the participant will no longer use abstinence as the selected contraception method, or if pregnancy is known or suspected in the participant or partner.

### **5.3.2. Meals and Dietary Restrictions**

- Participants must abstain from all food and drink (except water) at least 4 hours prior to any subsequent safety laboratory evaluations and 10 hours prior to the collection of the predose PK sample.
- For the fed period (Treatment E), a high-fat (approximately 50% of total caloric content of the meal), high-calorie (approximately 800 to 1000 calories) meal will be used for the evaluation of a food effect in this study. On Day 1 of the fed period (Treatment E) following an overnight fast of at least 10 hours, participants should begin breakfast approximately 30 minutes prior to Ritlecitinib administration. The breakfast will be consumed over approximately 20-minute interval with Ritlecitinib administered within approximately 10 minutes of completion of the meal. Participants must complete the entire breakfast. There are no water restrictions prior to and after dosing.
- For the fasted periods, water is permitted until 1 hour prior to study intervention administration. Water may be consumed without restriction beginning 1 hour after dosing. Non-caffeinated drinks (except grapefruit or grapefruit-related citrus fruit juices—see below) may be consumed with meals and the evening snack.
- Lunch will be provided approximately 4 hours after dosing.
- Dinner will be provided approximately 9 to 10 hours after dosing.
- In the fed periods, lunch and dinner will be provided at similar times to the fasting periods.
- An evening snack may be permitted.
- Participants will refrain from consuming red wine, grapefruit, or grapefruit-related citrus fruits (eg, Seville oranges, pomelos, fruit juices) from 7 days prior to the first dose of study intervention and during confinement in the CRU.
- While participants are confined, their total daily nutritional composition should be approximately 55% carbohydrate, 30% fat, and 15% protein. The daily caloric intake per participant should not exceed approximately 3200 kcal.

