### 3. OBJECTIVES AND ENDPOINTS

Objectives	Endpoints
Primary:	Primary:

 
To estimate the relative BA of ritlecitinib BiC when sprinkled on food (apple sauce, strawberry jam, and yoghurt) compared to intact BiC (reference) at a 30 mg dose under fasted conditions in adult healthy participants.
 
To estimate the effect of food on the relative BA of ritlecitinib intact BiCs at a 30 mg dose.
 
	
 
Plasma <math>AUC_{inf}</math> and <math>C_{max}</math> of ritlecitinib.
 

Secondary:	Secondary:

 
To evaluate the safety and tolerability of 30 mg BiCs of ritlecitinib administered to healthy adult participants under fasted and fed conditions.
 
	
 
S AE monitoring.
 

Tertiary/Exploratory:	Tertiary/Exploratory:

 
To characterize the PK parameters for ritlecitinib (BiCs) when sprinkled on food (apple sauce, strawberry jam, and yoghurt) compared to intact BiC (reference).
 
Validate the PK measurement of ritlecitinib in capillary blood samples collected using micro-sampling device against the PK measurement of ritlecitinib in venous blood samples.
 
To assess the sensory characteristics and overall palatability of sprinkled BiC by healthy participants.
 
	
 
<math>T_{max}</math>, <math>AUC_{inf}</math>, <math>t_{1/2}</math> (if data permit) and other PK parameters such as CL/F, <math>V_z/F</math>.
 
Ritlecitinib microsampling concentration versus plasma concentrations from venous blood samples.
 
CC1
 

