### 6.1.1. Administration

For **fasted** periods:

- Following an overnight fast of at least 10 hours, the participants will receive study intervention at approximately 08:00 hours (plus or minus 2 hours) without breakfast/standard meal on Day 1.

For **fed** period:

- Following an overnight fast of at least 10 hours, participants will receive breakfast approximately 30 minutes prior to dosing which is to be completed within approximately 20 minutes as outlined in [Section 5.3.2](#) (Meals and Dietary Restrictions). The participants will then receive study intervention at approximately 08:00 hours (plus or minus 2 hours).
- The participants will then receive study intervention at approximately 08:00 hours (plus or minus 2 hours). PF-06651600 should be administered within approximately 10 minutes of completion of the meal.

For **all** periods:

- Investigator site personnel will administer study intervention during each period with ambient temperature water to a total volume of approximately 240 mL. For treatments A and E only: Participants will swallow the study intervention whole, and will not manipulate or chew the study intervention prior to swallowing. Administer study intervention according to the IP Manual.

- In order to standardize the conditions on PK sampling days, all participants will be required to refrain from lying down (except when required for BP, pulse rate, and ECG measurements), eating, and drinking beverages other than water during the first 4 hours after dosing.

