Natural log transformed  $AUC_{inf}$  (if data permit),  $AUC_{last}$  and  $C_{max}$  will be analyzed using a mixed effects model with sequence and treatment as fixed effects and participant within sequence as a random effect. Estimates of the adjusted mean differences (Test-Reference) and corresponding 90% confidence intervals will be obtained from the model. The adjusted mean differences and 90% confidence intervals for the differences will be exponentiated to provide estimates of the ratio of adjusted geometric means (Test/Reference) and 90% confidence intervals for the ratios. Treatment A (intact BiCs) will be the Reference treatment and Treatment E (intact BiCs given with high fat meal) will be the Test treatment.

CCI  
[REDACTED]

[REDACTED]

[REDACTED]

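### Fed and fasted periods have different water rules around dosing, so the food-effect contrast E vs A carries a small uncontrolled difference besides the meal

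*Protocol*

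**What the plan says.** The effect of food is a primary objective (protocol section 3): "To estimate the effect of food on the relative BA of ritlecitinib intact BiCs at a 30 mg dose". It is estimated from one contrast (section 9.3.3, repeated in SAP section 6.1): "Treatment A (intact BiCs) will be the Reference treatment and Treatment E (intact BiCs given with high fat meal) will be the Test treatment". The model is a "mixed effects model with sequence and treatment as fixed effects and participant within sequence as a random effect".

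Section 5.3.2 sets the water rules in two consecutive bullets.

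- Fed period (Treatment E): "There are no water restrictions prior to and after dosing".
- Fasted periods (Treatments A to D): "For the fasted periods, water is permitted until 1 hour prior to study intervention administration". After dosing, "Water may be consumed without restriction beginning 1 hour after dosing".

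Two rules in section 6.1.1 apply to every period. The dose is given "with ambient temperature water to a total volume of approximately 240 mL", and participants must refrain from "eating, and drinking beverages other than water during the first 4 hours after dosing".

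**The concern.** Treatments A and E use the same 30 mg capsule and the same dosing water, so the contrast should isolate the meal. Section 5.3.2 adds a second planned difference: in E, participants may drink as much water as they like around dosing; in A, they may not.

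The protocol plainly wants matched conditions. Sections 5.3.4 and 6.1.1 restrict posture, food and drink for 4 hours in order to standardise the PK sampling days, and section 5.3.2 times the fed-period lunch and dinner to match the fasted periods. Water within an hour of the dose is left unmatched, with no stated reason.

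If extra water alters absorption, two things follow. The E/A ratio would reflect the meal plus the water. And because volume in E is left to each participant, it could add variability on the test side only. The post-dose hour in question contains the 0.25, 0.5 and 1 hour samples. Earlier studies of ritlecitinib found the food effect mainly on Cmax (section 2.2.4.2.1).

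**Working it through.** **Step 1: the rules side by side** (sections 5.3.2, 5.3.4 and 6.1.1)

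| Window | Treatment A (reference) | Treatment E (test) |
|---|---|---|
| Last hour before dose | No water | Unrestricted; breakfast starts about 30 minutes before dose |
| With the dose | About 240 mL | About 240 mL |
| First hour after dose | No water | Unrestricted |
| 1 to 4 hours after dose | Unrestricted; no other drinks | Unrestricted; no other drinks |

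The common 240 mL does not equalise the two hours around it. The 4-hour rule bars only drinks other than water, so it does not either. The difference is confined to a 2-hour window, and in E the extra water is allowed, not required.

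**Step 2: can the analysis recover it?** Every E dose is under one rule and every A dose under the other. The food-effect model (section 9.3.3; SAP Appendix 1) has sequence, treatment and participant only. Neither document asks for the volume of extra water to be recorded. The two effects are fully aliased, and no sensitivity analysis is possible afterwards. The IP Manual cited in section 6.1.1 might say more, but it is not available here.

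**Step 3: the planned precision, as a yardstick.** Inputs from section 9.5: n = 12; within-participant SD 0.226 (loge Cmax) and 0.117 (loge AUCinf).

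- Half-width from the stated interval at a ratio of 100%, ln(upper/lower)/2:
  - Cmax: ln(118.78/84.19)/2 = 0.172
  - AUCinf: ln(109.32/91.47)/2 = 0.089
- Reproduction, exp(± t × SD × √(2/12)). The best fit is 8 df (t = 1.8595):
  - Cmax: 84.23% to 118.72% (stated 84.19% to 118.78%)
  - AUCinf: 91.50% to 109.29% (stated 91.47% to 109.32%)
  - Both agree within rounding of the SDs.
- With 11 df (A and E alone, 12 participants; t = 1.7959), the Cmax half-width is 1.7959 × 0.226 × 0.4082 = 0.166, a factor of 1.18.

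**Step 4: what an assumed water effect would do.** The documents give no estimate, so the factor w below is purely an assumption. The observed ratio is the true ratio × w, and the relative shift is |ln w| divided by the stated half-width. The starting ratios 0.68 and 0.61 come from the Cmax reductions of about 32% (100 mg capsule) and 39% (50 mg tablet) in section 2.2.4.2.1.

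| w | 0.68 becomes | 0.61 becomes | Shift / Cmax half-width | Shift / AUCinf half-width |
|---|---|---|---|---|
| 0.90 | 0.61 | 0.55 | 0.61 | 1.18 |
| 0.95 | 0.65 | 0.58 | 0.30 | 0.58 |
| 0.975 | 0.66 | 0.59 | 0.15 | 0.28 |
| 1.025 | 0.70 | 0.63 | 0.14 | 0.28 |
| 1.05 | 0.71 | 0.64 | 0.28 | 0.55 |
| 1.10 | 0.75 | 0.67 | 0.55 | 1.07 |

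The AUCinf fractions are larger only because AUCinf is less variable. Nothing in the documents suggests that water changes the extent of absorption.

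**The case against.** The case against acting is substantial, and most of it stands.

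- **No effect is shown.** The documents do not say that water matters, in which direction, or by how much. Any range is a guess.
- **No conclusion hangs on a shift this small.** No hypothesis is tested and no margin is set (section 9.1; SAP section 5.1). Section 2.2.4.2.1 reports Cmax reductions of about 32% and 39% and still concludes that ritlecitinib may be taken with or without food.
- **The timing argument is weak.** A reader might infer that the peak is fixed in the first hour, so that Cmax must be affected. The documents describe rapid absorption but give no Tmax value, and they report a slight increase in Tmax with a high-fat meal. The peak in the fed period may well come later.
- **Harmonising is not automatically free.** A reader might infer that either existing rule could simply be applied throughout. Carrying the full fasted rule into E would mean eating an 800 to 1000 calorie breakfast, which must be finished, in about 20 minutes without water. Carrying the fed rule into A to D would loosen control in the three sprinkle contrasts, which are now standardised.

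These points limit the severity and shape the remedy. They do not remove the asymmetry: it is unexplained, unrecorded and aliased with treatment in a primary contrast. Any effect it has would be systematic, so more participants would not average it out.

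**Conclusion.** The point holds as a minor standardisation flaw. E vs A estimates the effect of the meal together with any effect of a different permitted water intake from 1 hour before to 1 hour after dosing. B, C and D vs A are unaffected, since all four treatments follow the fasted rule.

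The size is unknown. Under an assumed 2.5% to 5% change, the Cmax ratio would move by about 0.15 to 0.3 of its planned 90% CI half-width. A 5% change would be about 0.55 to 0.58 of the half-width for AUCinf. If participants drink little extra water in E, or if water has no effect, the shift is nil.

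Two stronger readings should be resisted. A reader might infer that the food-effect estimate is biased; the documents support only that an uncontrolled difference exists. A reader might also infer that matching the water would leave the meal as the only difference. It would not: E is always given in Period 5 and the food-effect model has no period term, so that separate confounding remains.

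**What to change.** Reconcile the two bullets in section 5.3.2, and carry the change into the site instructions:

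1. Let A and E follow the same water rule in the hour after dosing.
2. Breakfast falls within the hour before dosing, so set a standard volume for any water taken with the Treatment E breakfast and record what is drunk.
3. Leave Treatments A to D as they are.

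If the different rules are intended, state the reason and record the volume in E, so that the food-effect result can be read with it.

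The cost is a sentence or two of text, slightly less freedom to drink in Period 5, and one more item to record. No visit, sample or participant is added.

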### **5.3.3. Caffeine, Alcohol, and Tobacco**

- Participants will abstain from caffeine-containing products for 24 hours prior to the start of dosing and during confinement in the CRU.

- Participants will abstain from alcohol for 24 hours prior (or as specified above for red wine) to admission to the CRU and continue abstaining from alcohol and during confinement in the CRU. Participants may undergo an alcohol breath test or blood alcohol test at the discretion of the investigator.
- Participants will abstain from the use of tobacco- or nicotine-containing products for 24 hours prior to dosing and during confinement in the CRU.

#### **5.3.4. Activity**

- Participants will abstain from strenuous exercise (eg, heavy lifting, weight training, calisthenics, aerobics) for at least 48 hours prior to each blood collection for clinical laboratory tests. Walking at a normal pace will be permitted;
- In order to standardize the conditions on PK sampling days, participants will be required to refrain from lying down (except when required for BP, pulse rate, and ECG measurements), eating, and drinking beverages other than water during the first 4 hours after dosing;

